**COMPARISON OF THE VALIDITY AND RELIABILITY OF THREE
DIFFERENT METHODS USED FOR WRIST PROPRIOCEPTION
MEASUREMENT**

The most recently revised date: 06.25.2018

**The Human Subjects Protection Review Board
approbation date: 06.25.2018**

STUDY PROTOCOL

Participants

The prior sample size calculation section of G*Power 3.1.9.2 software revealed that the inclusion of 32 healthy participants (64 wrists) was necessary for achieving 95% power. Individuals who suffered an injury or underwent a surgical procedure in the last six months that could affect hand functions or senses were excluded from the study. Additionally, individuals with a history of neuromuscular disease, traumatic nerve injury, congenital anomalies, or skin infections were excluded. An informed consent form was obtained from all participants. An independent ethics committee approved the study (approval number:24074710--028).

Instrumentation

The Cybex isokinetic dynamometer [Cybex NORM®, Humac, CA, USA] was used as a reference standard to test the validity of the universal goniometer, inclinometer [Acumar, Lafayette Instrument Co., Lafayette, USA], and JPSG. The isokinetic dynamometer is a well-known instrument for measuring passive and active joint position sense (AJPS) and provides a target angle result without rater bias (Relph & Herrington, 2015). The Cybex isokinetic dynamometer has a good reliability in evaluating wrist AJPS (Seven et al., 2019).

Procedures

The evaluation of proprioception using the isokinetic dynamometer was performed with the participants in sitting. The shoulder was positioned in the midline, the elbow was flexed about 90°, and the wrist was positioned in supination (Brown, 2000). During the evaluation, the forearm was fixed with a strap to prevent the forearm from moving and changing the angle of the wrist. The rotation axis of the dynamometer was aligned with the diagonal axis of the distal tubercle of radius and the head of ulna (Figure 1). The

wrist was placed in a 0° position. In this starting position, the range of motion was set as 40° flexion and 40° extension (Ellenbecker et al., 2006). The device was calibrated before the evaluation of each participant.

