**COMPARISON OF THE VALIDITY AND RELIABILITY OF THREE
DIFFERENT METHODS USED FOR WRIST PROPRIOCEPTION
MEASUREMENT**

The most recently revised date: 06.25.2018

**The Human Subjects Protection Review Board
approbation date: 06.25.2018**

Statistical Analysis

Statistical analysis was performed using the SPSS version 28 (IBM, Armonk, NY) computer software system. The Normality of the variables was tested using the Shapiro-Wilk test. Since the data were non-parametric, the validity analysis was performed using Spearman's correlation test. The validity of these three methods was calculated according to their correlation with the isokinetic dynamometer data. Correlation coefficients was used to interpret the results. The correlation coefficient was defined as follows: between 0.90-1.00 was very high, between 0.70-0.90 was high, between 0.50-0.70 was medium, between 0.30-0.50 was weak, and less than 0.30 was negligible (Mukaka, 2012). The statistical significance level was determined as $p < 0.05$ for all analyses.

The Intraclass Correlation Coefficients $ICC_{3,1}$ (two-way mixed, absolute agreement) were calculated for test-retest reliability analysis. The $ICC_{2,1}$ value that was greater than 0.90 was defined as an excellent correlation, a good correlation between 0.75 and 0.90, a moderate correlation between 0.50-0.75 and a poor correlation if less than 0.50 (Koo & Li, 2016). Measurement errors of the three methods were used to calculate standard error of measurement (SEM) and Minimal Detectable Change (MDC) in a 95% confidence interval (Haley & Fragala-Pinkham, 2006; Suner-Keklik et al., 2017).

RESULTS

A total of 32 participants (64 wrists) were evaluated in the study (Figure 5). Demographic characteristics are presented in Table 1.

[figure not shown]

Table 1. Demographic features

	Minimum	Maximum	Mean ± S.D.
Age	19.00	31.00	23.34 ± 3.84
Height	160.00	193.00	173.66 ± 8.87
Weight	48.00	115.00	68.31 ± 13.75
BMI	17.56	33.97	22.52 ± 3.29

BMI: Body Mass Index

The results of the validity analysis of the methods are displayed in Table 2. The validity of these methods was found to be weak for the inclinometer and JPSG and moderately for the goniometer (Mukaka, 2012) (Table 2).

Table 2. The results of validity analysis and descriptive statistics of the methods

Methods	Median (25th per – 75th per)	r	P
Isokinetic dynamometer	3.17° (2.33° – 4.83°)	-	-
Inclinometer	3.66° (2.66° – 5.83°)	0.350	0.005*
Goniometer	3.50° (2.33° – 4.66°)	0.529	<0.001*

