JPSG	2.50° (1.66° – 3.33°)	0.432	<0.001*

per: percentile, r: correlation coefficient, °: degree, *: p<0.05

The results of the test-retest reliability analysis of the methods are displayed in table 3. The inclinometer was not found to be a reliable method for evaluating AJPS while the goniometer and JPSG were detected to have significant test-retest reliability. However, the 95% confidence intervals of the goniometer and JPSG were poor (Koo & Li, 2016) (Table 3).

Table 3. The results of test-retest reliability analysis and descriptive statistics

Methods	1st Measurement	2nd Measurement	ICC_{3,1}	P	SE M	MDC
	Median	Median				
	(25 per – 75 per)	(25 per – 75 per)				
Inclinometer	5.33° (3.33° – 8.17°)	4.50° (2.83° – 6.33°)	0.114	0.183	0.11	0.25
Goniometer	3.50° (2.33° – 5.66°)	3.66° (2.33° – 4.83°)	0.422	<0.001*	0.32	0.75
JPSG	2.33° (1.33° – 3.33°)	2.00° (1.33° – 3.33°)	0.369	0.001*	0.29	0.68

(per: percentile, r: correlation coefficient, °: degree, *: p<0.05)

The order in which each method was evaluated is presented in Table 4.

Table 4. The sequences of methods

Methods	First	Second	Third
Goniometer	23 (% 35.9)	24 (% 37.5)	17 (% 26.6)
Inclinometer	19 (% 29.7)	20 (% 31.2)	25 (% 39.1)
JPSG	22 (% 34.4)	20 (% 31.2)	22 (% 34.4)

REFERENCES

- Haley SM, Fragala-Pinkham MA 2006 Interpreting change scores of tests and measures used in physical therapy. *Physical therapy* 86, 735-743.
- Koo TK, Li MY 2016 A guideline of selecting and reporting intraclass correlation coefficients for reliability research. *Journal of chiropractic medicine* 15, 155-163.
- Mukaka MM 2012 A guide to appropriate use of correlation coefficient in medical research. *Malawi Medical Journal* 24, 69-71.

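### The study is titled a comparison of three methods, but no difference between methods is estimated; they are set apart by a band label (validity) and by significance (reliability)

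*SAP*

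**What the plan says.** The title of both documents opens with "COMPARISON OF THE VALIDITY AND RELIABILITY OF THREE". The SAP's Statistical Analysis section then handles each method alone: "The validity of these three methods was calculated according to their correlation with the isokinetic dynamometer data". Coefficients are read against fixed bands, of which the relevant ones are "between 0.50-0.70 was medium, between 0.30-0.50 was weak, and less than 0.30 was negligible". On testing it says only: "The statistical significance level was determined as $p < 0.05$ for all analyses".

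In the Results, the text before Table 2 labels the methods: "The validity of these methods was found to be weak for the inclinometer and JPSG and moderately for the goniometer". The text before Table 3 says: "The inclinometer was not found to be a reliable method for evaluating AJPS while the goniometer and JPSG were detected to have significant test-retest reliability". The SAP's own ICC scale calls anything below 0.50 poor, and all three ICCs (0.114, 0.422, 0.369) fall there.

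Neither document defines a difference between methods, a paired test or a contrast, for r or for ICC. Table 2 has no confidence intervals.

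**The concern.** Each reported P value answers whether one coefficient differs from zero. It does not answer whether one method does better than another, which is the question in the title. Two shortcuts fill the gap. For validity, methods are separated by which side of 0.50 the estimate falls; the goniometer's 0.529 is only 0.029 above that line. For reliability, they are separated by one ICC being non-significant while two are significant. A significant result beside a non-significant one does not show that the two differ.

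The design could support a proper answer. Per the Protocol's Procedures, the same rater used all methods on both limbs of each participant, with the order of methods randomised. Paired differences can be computed from data already collected. Without them, a reader choosing an instrument may take sampling noise for a difference.

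**Working it through.** **Inputs.** SAP Table 2: r = 0.529 (goniometer), 0.432 (JPSG), 0.350 (inclinometer). SAP Table 3: ICC = 0.422, 0.369, 0.114 in the same order. Sample: "A total of 32 participants (64 wrists) were evaluated in the study". The correlation between methods is not reported, so it is assumed. Two wrists of one person are not independent, so n = 64 is optimistic and n = 32 is shown as the other bracket.

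**1. Reproduce the printed P values.** For r, t = r√((n−2)/(1−r²)) with n = 64, two-sided:
- Inclinometer: 0.350 × √(62/0.8775) = 2.94, P = 0.005.
- JPSG: t = 3.77, P = 0.0004.
- Goniometer: t = 4.91, P < 0.001.

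For ICC, F = (1+ICC)/(1−ICC) on 63 and 63 degrees of freedom:
- Inclinometer: F = 1.26, P = 0.183.
- JPSG: F = 2.17, P = 0.001.
- Goniometer: F = 2.46, P < 0.001.

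All six match Tables 2 and 3. Each is a test of one coefficient against zero, on 64 wrists taken as independent.

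**2. Intervals for r.** 95% limits are tanh(atanh r ± 1.96 √((1+r²/2)/(n−3))), the Bonett-Wright form for Spearman coefficients.

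| Method | n = 64 | Bands covered | n = 32 |
|---|---|---|---|
| Goniometer | 0.31 to 0.69 | weak, medium | 0.20 to 0.75 |
| JPSG | 0.20 to 0.62 | negligible, weak, medium | 0.08 to 0.69 |
| Inclinometer | 0.11 to 0.55 | negligible, weak, medium | −0.01 to 0.63 |

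**3. Differences in r.** Meng's test for two correlations that share the dynamometer: z = (atanh r₁ − atanh r₂) √((n−3)/(2(1−c)h)). Here c is the inter-method correlation, m the mean of r₁² and r₂², f = (1−c)/(2(1−m)) and h = (1−fm)/(1−m).

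Example, goniometer against JPSG, n = 64, c = 0: m = 0.233, f = 0.652, h = 1.106, so z = (0.5888 − 0.4624) × √(61/2.212) = 0.66 and P = 0.51. Two-sided P, unadjusted, for c = 0 to 0.8:

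| Pair | Difference in r | n = 64 | n = 32 |
|---|---|---|---|
| Goniometer vs JPSG | 0.097 | 0.51 to 0.17 | 0.65 to 0.34 |
| JPSG vs inclinometer | 0.082 | 0.61 to 0.27 | 0.72 to 0.44 |
| Goniometer vs inclinometer | 0.179 | 0.24 to 0.013 | 0.42 to 0.085 |

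Goniometer against inclinometer reaches 0.05 at c of about 0.67 with n = 64.

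**4. Differences in ICC.** A rough Fisher-z contrast: z = (atanh ICC₁ − atanh ICC₂)/√(2(1−c)/(n−1.5)), where c is the assumed correlation between the two estimates, 0 to 0.5. Example, goniometer against inclinometer, n = 64, c = 0: (0.4501 − 0.1145)/0.1789 = 1.88, P = 0.06.

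| Pair | n = 64 | n = 32 |
|---|---|---|
| Goniometer vs inclinometer | 0.06 to 0.008 | 0.19 to 0.06 |
| JPSG vs inclinometer | 0.13 to 0.03 | 0.29 to 0.13 |
| Goniometer vs JPSG | 0.73 to 0.62 | 0.81 to 0.73 |

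**5. Scale.** The Protocol states that "the inclusion of 32 healthy participants (64 wrists) was necessary for achieving 95% power" but gives no effect size or test. By Fisher z, 64 units with 95% power correspond to testing a single r of about 0.40 (one-sided) or 0.43 (two-sided) against zero. If the observed differences were true, 80% power at c = 0.5 would need about 187 independent units for goniometer against inclinometer and about 594 for goniometer against JPSG.

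**The case against.** The best defence is that the study is descriptive: each method gets its own coefficient and label, no sentence names a best method, and the text goes on to call the goniometer and JPSG intervals poor. That stands in part. A reader might infer a printed ranking with the goniometer on top, but the documents do not state one; the contrast is implied by the labels and by the sentence setting the inclinometer against the other two. A purely descriptive aim would still sit badly with the title and with that sentence.

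A reader might also infer that the three methods do not differ. The figures do not support this. At n = 64, goniometer against inclinometer falls below 0.05 for validity if the methods correlate at about 0.67 or more. Both ICC contrasts with the inclinometer can fall below 0.05 if the estimates are moderately correlated. An untested difference is not an absent one.

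Nor do labels explain the reliability contrast: all three ICCs share one band, so only significance separates them. Finally, the ICC calculation is a rough approximation for an absolute-agreement coefficient, and a bootstrap with Holm adjustment is one valid remedy among several.

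**Conclusion.** The omission is certain: a study presented as a comparison specifies and reports no between-method contrast, and its wording separates the methods on grounds that are not evidence of a difference. Its effect on the conclusions is less certain. Under the assumptions shown, the goniometer and JPSG are not distinguished on validity or reliability, although one is labelled moderate and the other weak. Whether the inclinometer differs from the other two is open: the answer turns on correlations that are not reported and on how far two wrists of one person count as separate observations. The P values are approximations from printed coefficients and are unadjusted for multiplicity. The change should be made; it is not fatal to the study.

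**What to change.** Add to the SAP three pairwise differences in r and three in ICC. Give each a 95% confidence interval from a bootstrap that resamples participants, keeping both wrists and all methods of a person together. State how multiplicity is handled within each set of three, for example by Holm. Print a 95% interval beside every r in Table 2. Say that band labels are descriptive, and call one method better than another only where the estimated difference supports it; otherwise state that the methods were not distinguished. Reword the sentences before Tables 2 and 3 to match.

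Cost: some SAP wording and one bootstrap script on data in hand. The downside is slightly more analysis and a less definite contrast between methods.

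### The Table 2 inclinometer errors fit neither session in Table 3, no method's row fully matches, and the SAP does not say which session feeds the validity analysis

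*SAP*

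**What the plan says.** The protocol (Procedures) describes two sessions seven days apart. Within a session, a wrist's score is the average of its absolute errors over three trials. The repeat session is there to examine test-retest reliability.

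The SAP (Statistical Analysis) defines validity as the Spearman correlation of each method with the isokinetic dynamometer. It names neither a session nor a way of combining the two.

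The SAP Results then print, as median (25th – 75th percentile) in degrees:

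- Inclinometer: Table 2 "3.66° (2.66° – 5.83"; Table 3 first session "5.33° (3.33° – 8.17", second session "4.50° (2.83° – 6.33".
- Goniometer: Table 2 "3.50° (2.33° – 4.66"; Table 3 first session "3.50° (2.33° – 5.66", second session "3.66° (2.33° – 4.83".
- JPSG: Table 2 "2.50° (1.66° – 3.33"; Table 3 first session "2.33° (1.33° – 3.33"; second session median 2.00, quartiles 1.33 and 3.33.

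Table 3 has no dynamometer row, so the reference values in Table 2 cannot be traced to a session either.

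**The concern.** With two sessions and one defined score per wrist, each Table 2 row should equal a session in Table 3 or follow from a stated combination of the two. No row does so in full, and the inclinometer row is lower than both sessions throughout.

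The two tables carry the study's two aims. If they rest on different data, the inclinometer's validity coefficient (r = 0.350) and its reliability coefficient (ICC = 0.114) may not describe the same measurements. A reader also cannot tell which of two error levels for that instrument is right.

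**Working it through.** **Inputs.** All quartiles are from SAP Tables 2 and 3. The 32 participants and 64 wrists are from the SAP Results. The within-session score is from the protocol, Procedures.

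**1. Cell-by-cell comparison (degrees).**

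| Method | Quantity | Table 2 | Session 1 | Session 2 | T2 − S1 | T2 − S2 | Outside both? |
|---|---|---|---|---|---|---|---|
| Inclinometer | Q1 | 2.66 | 3.33 | 2.83 | −0.67 | −0.17 | yes |
| Inclinometer | Median | 3.66 | 5.33 | 4.50 | −1.67 | −0.84 | yes |
| Inclinometer | Q3 | 5.83 | 8.17 | 6.33 | −2.34 | −0.50 | yes |
| Goniometer | Q1 | 2.33 | 2.33 | 2.33 | 0 | 0 | no |
| Goniometer | Median | 3.50 | 3.50 | 3.66 | 0 | −0.16 | no |
| Goniometer | Q3 | 4.66 | 5.66 | 4.83 | −1.00 | −0.17 | yes |
| JPSG | Q1 | 1.66 | 1.33 | 1.33 | +0.33 | +0.33 | yes |
| JPSG | Median | 2.50 | 2.33 | 2.00 | +0.17 | +0.50 | yes |
| JPSG | Q3 | 3.33 | 3.33 | 3.33 | 0 | 0 | no |

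Six of nine quartiles lie outside both sessions. The gaps run down for the inclinometer and goniometer and up for the JPSG. For the inclinometer median, 1.67/5.33 = 31% and 0.84/4.50 = 19%. Rounding or truncating thirds (3.66 for 3.667) explains about 0.01°, not gaps of 0.16° or more.

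**2. Both sessions stacked.** The share of stacked values at or below any point is the average of the two session shares, so a stacked quartile must lie between the two session quartiles. This rules out stacking for all three inclinometer quartiles, and for at least one quartile of each other method.

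**3. Lower of the two sessions per wrist.** A per-wrist minimum cannot have a median above either session's median. The JPSG median of 2.50 exceeds both 2.33 and 2.00, so this rule cannot have been used for every method.

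**4. Per-wrist average of the two sessions.** This needs distributions the documents do not give. Assumptions: 64 wrists; log-normal, gamma or piecewise-linear distributions fitted to the Table 3 quartiles; 20,000 samples per setting.

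- Inclinometer: the expected median is 5.1–5.3°. A median at or below 3.66° occurred in 1 of 60,000 samples at a between-session correlation of 0.114, in 0 of 60,000 at −0.13 and in 3 of 60,000 at 0.35. All three quartiles were as low as Table 2 in none of the 180,000 samples.
- Goniometer (correlation 0.422) and JPSG (0.369): every Table 2 quartile lies inside the 99% simulation range, so averaging is possible.

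**5. How many values lie behind r.** With t = r√[(n − 2)/(1 − r²)] and r = 0.350:

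- n = 64: t = 0.350 × √(62/0.8775) = 2.94, two-sided p = 0.0046 (printed 0.005).
- n = 32: t = 0.350 × √(30/0.8775) = 2.05, p = 0.050.
- n = 128: t = 0.350 × √(126/0.8775) = 4.19, p = 0.00005.

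Allowing for rounding of r (0.3495 to 0.3505), only n = 62 to 64 gives 0.005. The correlation was therefore not run on 32 values or on 128. This does not fix the n behind the descriptive row.

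**6. A descriptive row from one limb only.** Drawing a random 32 of 64 wrists (same assumed distributions, 40,000 draws each), all three inclinometer quartiles were this low in 1.3–2.1% of draws from session 2, and in at most 1 of 40,000 from session 1. This is unlikely but not excluded.

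**7. Whether the ICC helps.** F = (1 + 0.114)/(1 − 0.114) = 1.257 on 63 and 63 df gives p = 0.183, as printed. That is the consistency formula, whereas the SAP states absolute agreement. With the same F and the session shift implied by the Table 3 quartiles, absolute agreement would give about 0.105–0.108. The check neither clears nor faults Table 3.

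**The case against.** The strongest reply is that only the inclinometer row is unexplained. The goniometer matches session 1 on two of three values, its third (4.66 against 5.66) could be a one-digit slip, and averaging could produce both its row and the JPSG row. The SAP does not promise that Table 2 repeats a session, so for these two methods the defect is an unstated source, not a failed calculation. The protocol also defines the within-session score, and its purpose for the repeat points to session 1 for validity. Finally, the printed coefficients and p values agree with each other at about 64 wrists, and the conclusions rest on r and ICC, not on descriptive quartiles.

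Much of this stands. The goniometer and JPSG gaps are supporting evidence only. The simulation counts depend on assumed distributions, and adding them over settings does not give a probability under any one model. The one-limb check used random halves, not a real right/left split. No coefficient is shown to be wrong.

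What it does not remove is the inclinometer conflict, which needs no model: three quartiles, each below both sessions. Nor does the hint toward session 1 settle the source, because Table 2 does not reproduce session 1 for any method.

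**Conclusion.** The concern holds. For the inclinometer, Table 2 cannot be session 1, session 2 or both stacked; this follows from the printed figures alone. A per-wrist session average is very unlikely, subject to the assumed distributions. A one-limb descriptive row is unlikely but possible, and the documents describe none. At least one printed figure is therefore wrong or comes from a source the documents do not describe.

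The discrepancy in the inclinometer median is 0.84° to 1.67°. The documents do not show which table is affected or whether the problem reaches r, ICC, SEM or MDC. If only a descriptive row was mis-keyed, every coefficient stands. This should be fixed because the tables for the two aims disagree and the SAP does not name the validity data; no changed conclusion has been demonstrated.

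**What to change.** - Trace Tables 2 and 3 to the wrist-level data.
- In Statistical Analysis, state the one session, or the one per-wrist combination of sessions, that supplies the validity data, and use it for all four instruments including the dynamometer.
- Recompute the Table 2 quartiles and the three Spearman correlations from that source, label the table with it, and check it against Table 3.
- If Table 3 proves to be the table in error, correct its quartiles, ICC, SEM and MDC.
- Revise the conclusions only if the coefficients change.

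The cost is a data check and a short re-run of existing analyses. No new data are needed, though reported coefficients may change.

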30° extension, which is the functional position of the wrist, was selected as the target angle for AJPS assessment (Neumann, 2002; Seven et al., 2019). After the test was explained to the participants, they were asked to actively bring the wrist from the neutral (0° flexion/extension) to 30° extension (a barrier was placed at 30° line) and wait for 5 seconds at this position. The participants were then asked to return to the starting position (a block was also placed at 0°). The participants were then asked to find the target angle. This trial was repeated three times. The amount of error between the target and achieved angles were recorded as the absolute angular error. The relative error amount was calculated using the arithmetic mean of these three absolute angular errors (Suner-Keklik et al., 2017). The same measurements were repeated for the other limb. The same rater performed all measurements.

All evaluations were repeated at the same hour of the day, seven days after the first measurement by the same rater to examine the test-retest reliability of the methods (Holmbäck et al., 1999). To avoid the learning effect (Feiring et al., 1990), the order which extremities were assessed (right/left) was determined using a web-based “Random Sequence Generator Application” (<https://www.random.org/sequences/>). The same randomization method was used to determine the order of the evaluation methods. The sequence used for each participant on the first evaluation was repeated on the second evaluation. A five-minute rest period was given between each measurement to eliminate the effect of muscle fatigue. As AJPS was demonstrated to significantly reduce during the menstruation period, the evaluation days of the female participants were arranged not to coincide with the week of menstruation (Aydoğ et al., 2005).

REFERENCES

- Brown LE 2000 Isokinetics in human performance. *Human Kinetics*.

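### All three test-retest ICCs are poor by the SAP's own 0.50 cut-off, yet the Results call two of them significant on a test against zero and never grade those two estimates

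*SAP*

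**What the plan says.** The SAP's Statistical Analysis section specifies a two-way mixed, absolute-agreement, single-measure ICC for test-retest reliability. It sets bands for reading it: above 0.90 excellent, 0.75 to 0.90 good, 0.50 to 0.75 moderate, and "a poor correlation if less than 0.50". The bands are printed for ICC(2,1) and Table 3 reports ICC(3,1). No other ICC values or bands appear, so I take the bands to be meant for Table 3. The same section sets a general significance level of 0.05 but does not say what value the ICC is tested against, or whether the test is one- or two-sided.

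Table 3 reports:

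| Method | ICC | P |
|---|---|---|
| Inclinometer | 0.114 | 0.183 |
| Goniometer | 0.422 | <0.001 |
| JPSG | 0.369 | 0.001 |

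The text above Table 3 reads "The inclinometer was not found to be a reliable method for evaluating AJPS", followed by "while the goniometer and JPSG were detected to have significant test-retest reliability". The next sentence adds, as a reservation, that "the 95% confidence intervals of the goniometer and JPSG were poor". The table as extracted has no interval column.

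Validity is reported differently. All three P values in Table 2 are below 0.05, but the text grades the methods by the size of the correlation: "The validity of these methods was found to be weak for the inclinometer and JPSG and moderately for the goniometer".

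**The concern.** The SAP sets a scale for reliability, and all three estimates fall in its lowest category. The Results nevertheless divide the methods into one that is not reliable and two with significant reliability. That division follows the P column and not the scale. A P value against zero shows only that repeat measurements are not wholly unrelated. It does not show that a method is reliable enough to use.

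Test-retest reliability is half of the study's question. A reader is told that the goniometer and JPSG have significant reliability, then that their intervals are poor, and is never told that both estimates are themselves poor. Such a reader could prefer these two methods on a label that the SAP's bands do not support.

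**Working it through.** **Inputs.** ICCs and P values from SAP Table 3; 32 participants and 64 wrists from the SAP Results; the 0.50 cut-off from the SAP's Statistical Analysis section. There are two occasions, seven days apart, and both wrists of each person are measured (Protocol, Procedures).

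**Step 1: apply the bands.** 0.114, 0.422 and 0.369 are all below 0.50. All three estimates are poor. This needs no further calculation.

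**Step 2: reproduce the P values.** For a single-measure ICC on two occasions, the test of ICC = 0 uses F = (1 + ICC)/(1 − ICC) on (n − 1, n − 1) degrees of freedom.

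| Method | F | One-sided P, n = 64 | Printed P | One-sided P, n = 32 |
|---|---|---|---|---|
| Inclinometer | 1.114/0.886 = 1.257 | 0.183 | 0.183 | 0.264 |
| Goniometer | 1.422/0.578 = 2.460 | 0.0002 | <0.001 | 0.007 |
| JPSG | 1.369/0.631 = 2.170 | 0.0012 | 0.001 | 0.017 |

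The n = 64 column matches Table 3. The n = 32 column does not, and neither do two-sided tests at n = 64 (0.366, 0.0005, 0.0025). So the printed P values are one-sided tests of ICC = 0 with the 64 wrists treated as independent.

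**Step 3: what that test lets through.** The smallest ICC that passes is (Fc − 1)/(Fc + 1), where Fc is the 95% point of F. At n = 64, Fc = 1.518 and the threshold is 0.518/2.518 = 0.206; at n = 32 it is 0.291. At a true ICC of t, the chance of passing is P[F > Fc(1 − t)/(1 + t)]. For t = 0.30 this is 79% (n = 64) or 52% (n = 32); for t = 0.40 it is 95% or 75%. Both true values are poor by the SAP.

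**Step 4: compare with 0.50.** An ICC of 0.50 corresponds to F = 1.5/0.5 = 3, so the one-sided P for ICC above 0.50 is P[F(n − 1, n − 1) > F/3]. For the 95% limits, divide and multiply F by its 97.5% point (1.646 at n = 64, 2.049 at n = 32) and convert back with (F − 1)/(F + 1). For example, goniometer, n = 64: 2.460/1.646 = 1.495 gives 0.198, and 2.460 × 1.646 = 4.050 gives 0.604. The n = 32 figures represent the extreme case in which two wrists carry no more information than one.

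| Method | P for ICC > 0.50 (n = 64; n = 32) | 95% CI, n = 64 | 95% CI, n = 32 |
|---|---|---|---|
| Inclinometer | 0.9996; 0.99 | −0.13 to 0.35 | −0.24 to 0.44 |
| Goniometer | 0.78; 0.71 | 0.20 to 0.60 | 0.09 to 0.67 |
| JPSG | 0.90; 0.81 | 0.14 to 0.56 | 0.03 to 0.63 |

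For the lower limit to reach 0.50, F must be 3 × 1.646 = 4.938, an estimate of 3.938/5.938 = 0.66 (0.72 at n = 32). The largest printed estimate is 0.422.

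**Step 5: sensitivity to the ICC form.** This F form is exact for a consistency ICC, whereas the SAP specifies absolute agreement. The documents do not give the ratio of session to error mean square that the latter needs. Assuming that ratio lies between 0 and 6, the absolute-agreement form at n = 64 gives P of 0.186 to 0.167, 0.0003 to 0.0001 and 0.0014 to 0.0007. The upper 95% limits are 0.338 to 0.351, 0.602 to 0.605 and 0.560 to 0.564. At n = 32 the upper limits are 0.416 to 0.446, 0.664 to 0.671 and 0.626 to 0.635. No band reading changes.

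**The case against.** The strongest reply is that the document has largely disclosed this. The sentence after the quoted clause applies the word poor to the goniometer and JPSG and cites the same guideline as the bands. Table 3 prints the estimates, and the cut-off is in the Statistical Analysis section. No sentence calls either method moderate or good, or recommends it. This stands as a partial concession. It does not cure the problem, because poor is attached to intervals that reach into the moderate band and withheld from estimates that lie below 0.50. Read loosely, it may describe the lower limits, which are poor.

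Second, significant is literally true under the SAP's general 0.05 level. That also stands, but being above zero does not answer a question for which the SAP has set a scale.

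Third, the inclinometer does look different: its approximate interval includes zero and lies wholly in the poor band, while the other two exclude zero (at both n = 64 and n = 32) and extend above 0.50. That is fair and should be kept in the corrected text. But the methods were not compared with each other, and one P above 0.05 with two below does not establish a difference in reliability.

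Finally, the null value is inferred and the intervals are approximate. The match to the printed P values is close, and the point does not depend on an interval column that may have been lost when the PDF was read.

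**Conclusion.** The concern holds. By the SAP's bands all three ICC estimates are poor, and no method is shown to reach moderate reliability. The headline wording for the goniometer and JPSG therefore needs to change from significant to poor, which affects two of the three methods on half of the study question.

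The grading of the estimates rests only on printed figures and on taking the bands to apply to the Table 3 ICCs. The statement that no method is shown to reach moderate reliability rests also on approximate intervals. It holds with 64 independent wrists, with 32 effective units, and across the assumed range for the absolute-agreement form. This has to be corrected, because the text as written leads with a conclusion that the SAP's scale does not support.

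**What to change.** Grade reliability by applying the SAP's bands to each ICC and its 95% confidence interval, as the Results already do by band for validity, and not by P below 0.05 against zero.

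- Add to Table 3 the 95% intervals computed from the data for absolute agreement, allowing for two wrists per person. The approximate limits above are no substitute.
- Replace the two sentences above Table 3 with wording such as: *All three ICC estimates are poor (below 0.50), and no method is shown to reach moderate reliability.* Follow it with one sentence that says, from the computed limits, whether each method's interval lies wholly below 0.50 or extends above it.
- If the P column stays, state that it tests ICC = 0, and draw no conclusion about differences between methods from it.

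The cost is two sentences and one table column, with no new data. The conclusion becomes less favourable to the goniometer and JPSG.
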